5.2. Definition of scheduled post-baseline measurements

Instead of relying solely on visit labels in the clinical database for post-baseline values, results collected on a date will be attributed to a specific time point by calculating the days relative to randomization. Listings will present all measurements.

Section 5.4 describes how time is calculated for each assessment.

5.2.1. Laboratory parameters

Post-baseline laboratory measurements are defined as the scheduled or unscheduled measurements collected closest to (or on) the patient’s target visit day ([Appendix D](#)), with collection date identified in the central laboratory data. If two assessments are equidistant from a

target study day, the earlier assessment is used. If the visit used for analysis includes two assessments on the same day, the average of the two measurements will be used. As with the baseline retest convention, if both the original and a retest result for a scheduled post-baseline laboratory are available in the central laboratory data, the original result will be used and the second (i.e., ‘retested’) result will be ignored. Otherwise, if the original result is not available (e.g., central laboratory detects an error) but a retest result is available, the retested result will be used as the scheduled post-baseline measurement.

5.2.2. Non-laboratory parameters

Post-baseline measurements of non-laboratory parameters are defined as the measurements collected on the day closest to the patient’s target visit day ([Appendix D](#)). If two assessments are equidistant from a target study day, the earlier assessment is used. If the visit used for analysis includes two assessments on the same day, the average of the two measurements will be used. The last clinic visits on and off study drug will be classified according to when they occurred as specified in [Section 5.2.3](#).

5.2.3. Last clinic visit and post-treatment results

Patients who terminate from the study before the Week 24 study visit should be brought back to the clinic as soon as possible for early termination assessments as well as a follow-up visit four weeks later. All assessments through Week 24 will be classified according to the time relative to randomization, regardless of the patient’s study participation or study drug status. Post treatment assessments will be classified according to the time relative to last dose in [Appendix D](#), for example 4 weeks off-treatment is within 7 to 35 days after last dose of the study.

Patients who discontinue treatment early but continue to be followed until the end of study will have their assessments attributed to visits as specified in [Section 5.2.1](#) and [Section 5.2.2](#).

A listing will indicate when each patient’s visits occurred. [Appendix D](#) indicates how scheduled results will be classified.

5.3. Handling of results of unscheduled tests

As discussed below in [Section 5.5](#), retests will be used for partial 6MWTs stopped for non-medical reasons and repeated at an unscheduled visit.

5.4. Definition of time

For visits (or events) that occur on or after randomization, time is calculated in days as:

$$\text{time} = \text{visit (or event) date} - \text{date of randomization} + 1$$

For visits (or events) that occur prior to randomization, time is calculated in days as:

$$\text{time} = \text{visit (or event) date} - \text{date of randomization}$$

The quantity ‘days since first dose’ is defined as:

- days since first dose = visit (or event) date – date of first + 1

The quantity ‘days since last dose’ is defined as:

days since last dose = visit (or event) date - date of last dose For summaries that present distribution of time expressed in weeks and months, weeks will be defined as days divided by seven and months as days divided by 30.4375.

5.5. Missing and partial data

Early termination of the 6MWT may be due to one of the six American Thoracic Society (ATS) immediate stopping criteria, low oxygen, or elective non-medical reasons. When a partial 6MWT is caused by non-medical reasons (e.g., a bathroom break), the patient is encouraged to return for an unscheduled visit to redo the 6MWT.

For the analysis of safety variables, only partial dates may be imputed; otherwise, missing data will be treated simply as missing.

The central laboratory uses assays that have lower limits of detection (LLD). All laboratory results below the LLD will be imputed as 1/2 of the LLD. Results reported as greater than a value (i.e., '> value') will be imputed as $1.0 \times$ that value. In the event that a large percentage (> 20% of values) of laboratory values are out of the range of the limits of detection, then a footnote will be added to indicate that the percentage of values falling outside of the limits of detection is greater than 20%.

6. DATABASE LOCK AND UNBLINDING

6.1. Final database lock

After the database lock and the authorization for unblinding (Section 6.2), the treatment codes will be merged to the analysis datasets. Any change to the clinical database after this time will require written authorization, with explanation, by Reata. In addition, beginning at the time of database lock, an audit trail will be maintained of all versions of the analysis datasets that may result from refinements of the algorithms for derived variables in the course of the analysis.

6.2. Authorization for unblinding

After database lock and upon receipt of written authorization from Reata, a blinded study team will receive the actual treatment codes directly from the group maintaining the IWRS. This team will generate top-line results and provide them to Reata along with the analysis files containing the randomized treatment codes. Reata will not have direct access to the randomized treatment codes until they have been provided the top-line results and datasets.

Reata's standard operating procedures dictate how access to the treatment codes will be extended within the company and to investigative sites.

7. PATIENT SUMMARIES

7.1. Enrollment

Enrollment will be summarized by country and geographical region. A table will present the number and percentages of patients in each stratum by treatment group.

7.2. Disposition

The disposition of patients (number randomized, study drug exposure, duration of follow-up, and inclusion in the various study populations) will be tabulated by treatment group in the ITT and Safety populations. Completion of study treatment, completion of study, discontinuation of study drug, discontinuation of study, and reason for discontinuation of study drug treatment and study will be summarized. See Section 8.2 for other summaries of treatment exposure. Time to permanent study drug discontinuation will be summarized. If the treatment end date or study end date are missing, the date will be imputed as the Study Drug Termination (SDT). If the treatment end date or study end date are missing and no reason for treatment or study discontinuation are included in the CRF, the reason for treatment or study discontinuation will be study termination.

7.3. Demographic and baseline characteristics

Summaries of demographic and other baseline characteristics will be presented by treatment group for all analysis populations (Section 3). The two treatment groups will be assessed descriptively for comparability of demographic and baseline characteristics for the ITT study population. Demographics and baseline characteristics will be summarized by subgroups.

Demographics and other baseline characteristics include the following:

- age (years) at the date of informed consent, sex, ethnicity, race
- height, weight, body mass index (BMI)
- baseline disease characteristics (e.g., WHO functional class, baseline 6MWT, years since PAH diagnosis)
- connective tissue disease (CTD) etiology (scleroderma, lupus, mixed, and other)
- pulmonary function testing results
- PAH and CTD medications
- geographic region
- baseline eGFR
- baseline eGFR category
 - ≥ 90 (ml/min/1.73m²)
 - 60 to < 90 (ml/min/1.73m²)
 - 45 to < 60 (ml/min/1.73m²)
 - 30 to < 45 (ml/min/1.73m²)
 - 15 to < 30 (ml/min/1.73m²)
 - < 15 (ml/min/1.73m²)
- other variables of interest

7.4. Medical history

Medical history is summarized by treatment. Medical history is coded using MedDRA (Medical Dictionary for Regulatory Activities) version 19.0. Medical history items are summarized by MedDRA SOC and PT.

8. STUDY DRUG AND OTHER MEDICATIONS

8.1. Prior and concomitant medications

All concomitant medications collected from screening through the end of the study will be classified by preferred terms according to the WHO Drug Dictionary (version 01MAR2016, type DDE+HD, format B2). Concomitant medications will be summarized by WHO Drug Dictionary classification. Special groups of medications (e.g. PAH, CTD) will be summarized by treatment group, by medical history as appropriate, and dose, if feasible.

8.2. Duration of treatment and exposure to study drug

The study drug will be supplied in tamper-evident kits containing two 30-cc high-density polyethylene (HDPE) bottles. Each bottle will utilize foil induction-seal liners and a child-resistant closure. Each bottle of study drug will contain 30 capsules of 2.5 mg or 5 mg strength bardozone methyl or the matching placebo capsules. Duration of treatment will be defined for each patient as the number of days the patient received study medication [(date of last dose) – (date of first dose) + 1]. Total number of administered doses will be calculated for each patient using duration of treatment minus missed doses. Missed doses are calculated from 30-count bottles and number of expected doses based on treatment duration. For example, a patient returning 3 capsules in each bottle after 28 days of treatment is assumed to have administered 27 doses and missed 1 dose. Since two bottles are included in each kit, if the number of returned capsules in each bottle is not equal, the bottle with the maximum number of returned capsules will be used for calculating missed doses. Total number of doses dispensed and total dose (mg) dispensed are calculated from total number of kits (bottles) recorded on the Study Drug Dispensation eCRF. Total number of doses received are calculated from information on the eCRF of Study Drug Return and Study Drug Dispensation, as the total number of doses dispensed – total number of doses returned. Study drug compliance (%) is calculated as $100 \times \text{total number of doses received} / \text{total number of doses dispensed}$. The proportion of patients who have $\geq 80\%$ compliance is summarized. To summarize the actual dose-titration, frequency counts and percent of patients on each dose-level (as determined by the dispensed kit strength) will be tabulated for each scheduled dispensing visit.

Standard descriptive statistics will be used to summarize duration of treatment, number of doses administered, number of missed doses, percent treatment compliance, and total exposure. Descriptive statistics will be calculated and tabulated by treatment group and study completion status for the ITT study population, and if warranted, for the other study populations. All dosing information will be listed by treatment group and patient ID. Study drug administration over time will be summarized in a listing showing study drug dispensed at each clinic visit.

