9.10.18. Study Drug Dispensation and Collection

Study drug will be dispensed to the patient and collected from the patient as indicated in [Table 3](#). The patient will be dispensed one treatment kit at Day 1 and Week 4; two treatment kits will be dispensed at Week 8 and Week 16. Dispensed treatment kits from each visit should be returned to the site for collection at the subsequent visit.

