10.5. Study Drug Accountability

The investigator, or designee, will maintain a record of all study drug received, dispensed, and returned to the Sponsors' designee. No study drug shall be destroyed by the clinical site unless directed in writing to do so by the Sponsor's quality assurance department. Study drug bottles and any unused capsules should be returned to the study staff for eventual disposition by the Sponsor. The number of capsules returned at each visit will be recorded for each bottle in the kit.

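### SAP 8.2 divides doses received by doses dispensed, and 180 are supplied for 168 expected, so the planned surplus counts as non-compliance and a completer who takes every dose scores 93.3%

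*SAP*

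**What the plan says.** SAP 8.2 counts doses dispensed from the kits recorded as handed out. It then says: "Total number of doses received are calculated from information on the eCRF of Study Drug Return and Study Drug Dispensation", as dispensed minus returned. The percentage follows: "Study drug compliance (%) is calculated as" 100 times received over dispensed. The share of patients at 80% or more is summarised, and the exposure statistics are "tabulated by treatment group and study completion status for the ITT study population".

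The same section counts missed doses on another basis: "Missed doses are calculated from 30-count bottles and number of expected doses based on treatment duration". Its example is that "a patient returning 3 capsules in each bottle after 28 days of treatment is assumed to have administered 27 doses and missed 1 dose".

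On supply, Protocol 9.10.18 dispenses "one treatment kit at Day 1 and Week 4; two treatment kits will be dispensed at Week 8 and Week 16", and adds: "Dispensed treatment kits from each visit should be returned to the site for collection at the subsequent visit". Protocol 10.5 says likewise: "Study drug bottles and any unused capsules should be returned to the study staff". Protocol 9.4 and SAP 2.2.1 both set 168 expected doses and call a patient treatment-compliant at 126 or more of them.

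**The concern.** A ratio of received to dispensed measures adherence only if the supply equals the doses due. Here each scheduled dispensing exceeds the doses due before the next nominal visit. The excess is subtracted from the numerator as returned stock but stays in the denominator.

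The exposure table would then show a compliance percentage at odds with the missed-dose count beside it: no missed doses next to 93.3%. The 80% summary would apply a stricter cut than its label suggests. For patients who stop drug early, the percentage would mostly reflect when the last kit was handed out. The split by study completion status does not isolate these patients, because those who stop drug are asked to stay in the study (Protocol 8.4.1, SAP 2.2.2).

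**Working it through.** **Inputs**

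- Doses per kit: two 30-capsule bottles (SAP 8.2), one capsule from each per day (Protocol 9.10.17), so 30 daily doses.
- Kits: 1, 1, 2 and 2 at Day 1 and Weeks 4, 8 and 16 (Protocol 9.10.18).
- Expected doses: 168 (Protocol 9.4, SAP 2.2.1).
- Leftovers returned (Protocol 9.10.18 and 10.5).

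**The plan's own figures reproduce.** Example patient: 30 − 3 = 27 administered and 28 − 27 = 1 missed. Treatment-compliant rule: 0.75 × 168 = 126.

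**Supply against need, nominal visit days**

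| Interval | Dispensed | Due | Surplus | Due / dispensed |
|---|---|---|---|---|
| Day 1 to Week 4 | 30 | 28 | 2 | 93.3% |
| Week 4 to Week 8 | 30 | 28 | 2 | 93.3% |
| Week 8 to Week 16 | 60 | 56 | 4 | 93.3% |
| Week 16 to Week 24 | 60 | 56 | 4 | 93.3% |
| Total | 180 | 168 | 12 | 93.3% |

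**Completer with no missed dose.** 168/180 = 93.3%. With the ±3-day Week 24 window, a last dose on Day 165 gives 165/180 = 91.7% and on Day 171 gives 171/180 = 95.0%. Counting capsules instead of doses changes nothing: 336/360 = 93.3%.

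**The 80% cut.** 0.80 × 180 = 144 doses. This is 144/168 = 85.7% of expected doses (144/165 = 87.3% to 144/171 = 84.2% across the window). Against 168 the cut would be 0.80 × 168 = 134.4, so 135 doses. Completers taking 135 to 143 doses fall below 80% only because of the surplus.

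**Example patient.** 27/30 = 90.0% by the compliance formula; 27/28 = 96.4% on the missed-dose basis.

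**Early stoppers, no missed dose, leftovers returned**

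| Last dose | Dispensed | SAP score | On-treatment adherence | Share of 168 |
|---|---|---|---|---|
| Day 14 | 30 | 14/30 = 46.7% | 100% | 14/168 = 8.3% |
| Day 28, Week 4 kit not dispensed | 30 | 28/30 = 93.3% | 100% | 28/168 = 16.7% |
| Day 28, Week 4 kit dispensed | 60 | 28/60 = 46.7% | 100% | 28/168 = 16.7% |
| Day 84 | 120 | 84/120 = 70.0% | 100% | 84/168 = 50.0% |

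The SAP score matches neither on-treatment adherence nor the share of planned doses taken.

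**The case against.** The arithmetic is hard to dispute; the case on the other side is about weight.

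- **Little depends on the percentage.** No efficacy analysis or analysis population uses it, and extension eligibility has its own 126-of-168 rule. SAP 8.2 also tabulates duration, doses administered and missed doses, and SAP 7.2 summarises drug discontinuation and time to it, so early stopping can be seen elsewhere. This stands and is why the point is minor. One loose end is that SAP 14.1 lists major deviations in treatment compliance without saying which measure applies.
- **Among completers the effect is uniform.** The nominal factor of 0.933 applies in both arms, a perfect completer still passes 80%, and only the 135-to-143-dose band changes class. This stands for completers who return all leftovers. It does not cover early stoppers.
- **The surplus per interval is nominal.** A Week 4 visit on Day 31 can use up the first kit. True, but the total is still 180 against 168, with the 91.7% to 95.0% range above.
- **The formula is explicit, and supply-based and duration-based figures are different measures.** True as a matter of definition. But a measure labelled compliance that cannot reach 100% on the nominal schedule when leftovers are returned is poorly chosen, and the section already holds a better denominator.
- **A duration denominator can exceed 100%.** If nothing from the first kit is returned after 28 days, the ratio is 30/28 = 107.1%. This is fair, but the gap already exists: the missed-dose count would be −2, and the present formula would score 30/30 = 100% by treating unreturned capsules as taken.

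**Conclusion.** The compliance formula is wrong for this dispensing schedule, with low consequence. It understates a perfect completer by 6.7 percentage points (100 − 93.3), raises the effective 80% cut to 85.7% of expected doses, and gives early stoppers scores driven by the kit cycle.

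The results assume scheduled kits only and return of all unused capsules. The total of 180 is not printed in the documents; it follows from kit content and schedule. How many patients would be affected cannot be determined from the documents, nor whether early stopping would differ by arm.

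The 126-dose rule is a separate matter. A completer with exactly 126 doses scores 126/180 = 70.0% under SAP 8.2 and 75.0% of 168. That patient is below 80% on either denominator, so the case shows that the two measures need distinct names rather than harm from the formula.

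**What to change.** In SAP 8.2, define compliance (%) as 100 × total doses administered / doses expected over the treatment duration (date of last dose − date of first dose + 1), and apply the 80% summary to that ratio. The perfect completer then scores 168/168 = 100%, the example patient 27/28 = 96.4%, and an early stopper with no missed dose 100%.

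Add a sentence saying that this is descriptive on-treatment adherence, distinct from the 126-of-168 treatment-compliant rule in SAP 2.2.1 and Protocol 9.4. It would be sensible at the same time to say how unreturned capsules are counted and which measure SAP 14.1 uses.

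The cost is one formula and one clarifying sentence, plus those two short clarifications if adopted. Numerator and denominator are already derived in SAP 8.2, and no new data are needed.

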9. ESTIMATED GLOMERULAR FILTRATION RATE (EGFR)

Estimated glomerular filtration rate (eGFR) value will be calculated at the central laboratory and used in data analyses. The equation used to calculate eGFR for each patient will be the Chronic Kidney Disease Epidemiology Collaboration (CKD-EPI) equation:

$$\bullet \text{ eGFR (mL/min/1.73 m}^2\text{)} = 141 \times \min(\text{Scr}/\kappa, 1)^\alpha \times \max(\text{Scr}/\kappa, 1)^{-1.209} \times 0.993^{\text{Age}} \times 1.018 \text{ [if female]} \times 1.159 \text{ [if black]}.$$

Where Scr is serum creatinine (mg/dL), κ is 0.7 for females or 0.9 for males, and α is -0.329 for females or -0.411 for males, and Age is the age at Screening. Min indicates the minimum of Scr/ κ or 1, and max indicates the maximum of Scr/ κ or 1.

Missing eGFR values will not be imputed for the analysis of efficacy.

10. EFFICACY OUTCOMES

10.1. Primary efficacy outcome

The primary efficacy variable is the change from baseline in 6MWT.

10.2. Secondary efficacy outcome

The secondary efficacy outcome is the time-to-first persistent clinical improvement event. To declare that clinical improvement has occurred, at least one of the following four criteria must be met:

1. Improvement by at least one WHO functional class coupled with no more than a 15% decrease from baseline in 6MWT.
2. Increase from baseline in 6MWT by at least 10% and stability or improvement in the WHO functional class.
3. Decrease from baseline in creatine kinase (a surrogate biomarker for muscle injury and inflammation) by at least 10% and no worsening in WHO functional class and no more than a 15% decrease from baseline in 6MWT.
4. Improvement in estimated glomerular filtration rate (eGFR) $\geq 10\%$ of baseline.

The persistence of the change in WHO functional class, 6MWT, eGFR, or creatine kinase must be confirmed by a subsequent assessment that also meets the defined criteria. The confirmatory assessment must occur at least 14 days after the initial assessment, or at the next scheduled assessment. If persistent improvement is confirmed, the date of the event will be considered the initial assessment of improved WHO functional class, 6MWT, eGFR, or creatine kinase.

If confirmatory observation of initial improvement is not available for any reason, such as end of study or death, it may or may not be considered an event as defined by the timing of improvement as it relates to other study events. Below is a list of possible reasons for failure to obtain a confirmatory observation along with the adjustment to the definition of improvement.

These reasons are as follows:

1. Last visit: If the improvement is observed at the last scheduled assessment, the requirement for an additional assessment after 14 days is waived, and the patient is classified as satisfying the criteria for improvement. In the absence of study end date, Study Drug Termination (SDT) is used.
2. Death: If the patient's death occurs before the confirmatory observation, then the patient is classified as not satisfying the criteria for improvement.
3. Study termination: If the patient terminates the study for reasons of "lost to follow-up" or "withdrawal of consent", then the patient is classified as not satisfying the criteria for improvement.
4. Patient starts new PAH drug: If a patient decides to stop study drug and switch to a new PAH drug, then the patient is classified as not satisfying the criteria for improvement.
5. Patient discontinues study drug: If a patient discontinues the study drug due to an AE and improvement is confirmed, then the patient is classified as satisfying the criteria for improvement. If improvement is not confirmed or if the patient has no follow-up measurement, then the patient is classified as not satisfying the criteria for improvement.

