11. STATISTICAL METHODS

11.1. Primary efficacy outcome

11.1.1. Primary analysis

This section describes the methods planned for the primary analysis, which is based on the primary efficacy outcome, the change from baseline in 6MWT. The analysis will compare the mean change in the bardoxolone methyl group relative to placebo at Week 24. A mixed model will be fit with this outcome using the following PROC MIXED code in SAS, where ID is the patient identifier, SCR_6MWT and DELT_6MWT are the screening values for the 6MWT and change from baseline, respectively, in the primary outcome at each visit (VOBS) by treatment group (GRP), and N_PAH_MEDS is the fixed number of background PAH therapies for a patient. Below is example code used to estimate the treatment effect:

```
proc mixed data = &DAT. method=reml alpha=0.05 covtest;
  class ID GRP (ref="plc") VOBS (ref=LAST)
    N_PAH_MEDS;
  model DELT_6MWT = SCR_6MWT
                    N_PAH_MEDS
                    GRP
                    VOBS
                    GRP * VOBS
                    VOBS * SCR_6MWT Hb / s ddfm=kr;
  repeated VOBS / subject = ID type = UN r;
  lsmeans VOBS * GRP / diff om cl e;
run;
```

The model will have the following characteristics:

- The response variable will be the vector of observed change in the primary efficacy outcome from baseline at each study visit where the 6MWT is measured (Week 4, Week 8, Week 16, and Week 24). The outcome will consist of the following four repeated measures: Week 4 6MWT – baseline 6MWT, Week 8 6MWT – baseline 6MWT, Week 16 6MWT – baseline 6MWT, and Week 24 6MWT (averaged over both measurements made at Week 24) – baseline 6MWT. [REDACTED] 6MWT values collected after the date of clinical worsening will be treated as missing for analysis of 6MWT.
- Repeated post-baseline measurements from each patient will be identified by patient identifier (ID).
- Within-patient correlations will be modeled using an unstructured covariance structure. In the unlikely situation that this model does not converge (i.e., the study has too few observations for the number of parameters estimated), the model will use the heterogeneous Toeplitz structure, which assumes the correlation between two repeated measurements depends solely on their lag in visit number, and that the variance of the outcome may differ over time. If the model still does not converge

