11.2. Secondary efficacy outcome

The secondary efficacy outcome, the time to clinical improvement, will be analyzed using methods for a censored time-to-event outcome. All analyses will be stratified using number of background PAH medications at baseline to define the strata.

Summary tables will present median time to first clinical improvement and associated 95% CIs for each treatment group as well as hazard ratios and 95% CIs for each comparison of bardoxolone methyl to placebo. Median duration with appropriate 95% CIs, as well as the proportion of patients remaining event-free at times of interest, will be estimated using Kaplan-Meier methods with the product limit estimator computed using PROC LIFETEST in SAS.

PROC PHREG in SAS will be used to estimate hazard ratios, mean and standard error time -to-event, and their 95% CIs by Cox regression models.

[REDACTED]

In the event that the number of events across strata is too small, the strata consisting of zero background PAH medications and one background PAH medication will be collapsed.

[REDACTED]

[REDACTED]

Treatment group comparisons will use the Type 3 Chi-square test and unadjusted two-sided p-value associated with the treatment group variable in the Cox proportional hazards model. Time-to-event analyses will use Breslow's method of handling ties in event times [1], which is the default method used in PROC PHREG. The TEST statement in PROC LIFETEST will be used to include the strata and the STRATA statement will be used in PROC PHREG.

Kaplan-Meier plots will supplement these presentations. The number of patients within each treatment group at risk of an event at regular time points will appear at the bottom of these figures.

The secondary outcome is important in understanding the effectiveness of bardoxolone methyl and its ability to improve function.

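### The eGFR criterion in the secondary composite (SAP 10.2, criterion 4) has no WHO-class or 6MWT condition, although the other three criteria each have one

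*SAP*

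**What the plan says.** SAP 10.2 defines the secondary outcome as time to first persistent clinical improvement. Any one of four criteria is enough:

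- **Criterion 1**, better WHO class, applies only when "coupled with no more than a 15% decrease from baseline in 6MWT".
- **Criterion 2**, a 6MWT gain of at least 10%, also requires "stability or improvement in the WHO functional class".
- **Criterion 3**, a CK fall of at least 10%, also requires "no worsening in WHO functional class and no more than a 15% decrease from baseline in 6MWT".
- **Criterion 4** is "Improvement in estimated glomerular filtration rate (eGFR" of at least 10% of baseline. Nothing is attached to it.

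All four need confirmation at least 14 days later or at the next scheduled assessment. If improvement is first seen at the last scheduled assessment, "the requirement for an additional assessment after 14 days is waived". The same rule adds: "In the absence of study end date, Study Drug Termination (SDT) is used".

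SAP 11.2 calls the outcome "important in understanding the effectiveness of bardoxolone methyl and its ability to improve function".

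Protocol 6.2.2 has three components (WHO class, 6MWT, CK), no eGFR component and no functional conditions. SAP 17 discloses the eGFR addition, but it presents the conditions on criteria 1 to 3 as protocol wording.

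**The concern.** The SAP does not accept a CK fall as improvement in a patient whose function has declined. It accepts an eGFR rise in the same patient, and the readable text gives no reason for treating the two biomarkers differently. An event on the only secondary efficacy outcome can therefore mean that a patient walks less far, or is in a worse functional class, while serum creatinine has drifted down. What is at stake is the meaning of an event on an endpoint that the SAP presents as informative about function.

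**Working it through.** **1. Which routes are open to a functionally worse patient**

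| Criterion | WHO class worse | 6MWT down by more than 15% |
|---|---|---|
| 1, WHO class | closed: needs a better class | closed by its 6MWT condition |
| 2, 6MWT | closed by its WHO-class condition | closed: needs a 10% gain |
| 3, CK | closed | closed |
| 4, eGFR | **open** | **open** |

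The persistence rule and the rules for missing confirmation apply to all four criteria and are not functional conditions. This step needs no assumption.

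**2. What a 10% eGFR rise means in creatinine**

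SAP 9 gives the eGFR equation. The required creatinine ratio is 1.10^(−1/e), where e is the size of the exponent.

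- Above kappa, e = 1.209: ratio 0.924, a fall of 7.6%.
- Below kappa, women, e = 0.329: ratio 0.748, a fall of 25.2%.
- Below kappa, men, e = 0.411: ratio 0.793, a fall of 20.7%.

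The eGFR at the kappa boundary is 141 × 0.993^age, times 1.018 for women. At age 60 that is about 94 (women) and 93 (men); at age 40, about 108 and 106.

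**3. Illustration of size**

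The documents state neither eGFR variability nor the share of patients who become functionally worse, and they give no figure to reproduce. Assumed inputs:

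- share functionally worse throughout, f = 5–20%, independent of eGFR;
- within-patient eGFR CV of 5% or 7%, lognormal, creatinine above kappa;
- baseline the mean of two values (SAP 5.1 uses a mean);
- chemistry at Weeks 1, 2, 4, 6, 8, 16 and 24 (protocol Table 3);
- event = ratio of at least 1.10 at two successive visits, or at Week 24 alone;
- 65 patients per arm (SAP Appendix B).

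Because a functionally worse patient fails criteria 1 to 3, added events = f × P(eGFR event). P comes from 400,000 simulated patients.

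| True eGFR change | P at CV 5% / 7% | Added, % of patients | Added, of 65 |
|---|---|---|---|
| None | 8.7% / 20.5% | 0.4–4.1 | 0.3–2.7 |
| +5% | 35.5% / 46.1% | 1.8–9.2 | 1.2–6.0 |
| +10% | 73.2% / 73.0% | 3.7–14.6 | 2.4–9.5 |

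For example, 0.20 × 20.5% = 4.1%, and 4.1% of 65 = 2.7.

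**4. Below kappa**

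The same creatinine noise gives a smaller eGFR CV: 5% × 0.329/1.209 = 1.4% at the low end and 7% × 0.411/1.209 = 2.4% at the high end. With no true change, P is then 0.00–0.06%. Multiplied by 20%, the added share is at most about 0.01% of patients.

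**5. Type I error**

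The composite log-rank test was simulated with no eGFR effect (65 per arm, 1,000 trials per setting, standard error about 0.7 points). It gave p < 0.05 in 3.9–6.1% of trials without the condition and 3.9–6.9% with it. Both ranges are consistent with 5%.

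**The case against.** **Effect and inputs.** The illustration is close to an upper bound. It places patients above kappa and treats functional worsening as lasting throughout, for which the documents give no figure. Because the outcome is time to first event, a patient who meets criteria 1 to 3 before worsening gains nothing from criterion 4. Confirmed clinical worsening is also a listed reason to stop study drug (protocol 8.4.1), and adding PAH therapy depends on it (9.10.5). A switch to a new PAH drug before confirmation is a non-event under rule 4 of SAP 10.2. All of this stands, and it is why the range begins near zero.

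**Precedent.** The protocol's CK component has no functional condition, and the eGFR addition is disclosed. That is true, but the governing SAP did condition CK, so the inconsistency lies within the SAP.

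**Redactions.** Parts of SAP 11.2, 11.3.4 and 17 cannot be read. They may hold a sensitivity analysis or a censoring rule. The four criteria themselves are fully readable in 10.2.

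**Stronger readings that the documents do not support:**

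- *The gap favours active treatment or inflates Type I error.* That would require a drug effect on eGFR, and no readable passage states one. The +5% and +10% rows are hypothetical. With no effect, the extra events fall equally in both arms.
- *The missing condition accounts for all the eGFR events.* The 9–21% event probability with no effect describes including eGFR at all. Under the assumed f, 80–95% of those events are in functionally stable patients, and the condition would leave them in place.
- *The last-visit waiver turns early terminations into events.* If data end at Week 8 with no eGFR change, P is 7.7–18.0% with the waiver and 3.1–9.7% without. But rules 2 to 5 of SAP 10.2 already class unconfirmed improvement as a non-event after death, loss to follow-up, withdrawal of consent, a new PAH drug or discontinuation for an adverse event. The first three are the only termination reasons in protocol 8.4.2. The higher figure could apply only to a narrow group, such as patients whose missing end date is set to Study Drug Termination.

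**Conclusion.** The concern holds as a flaw in the endpoint definition and should be fixed. Criterion 4 alone lacks a functional condition, so a functionally worse patient can be reported as clinically improved. That conclusion rests on the text of SAP 10.2 alone.

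Its size is not known. Under the assumed inputs and no drug effect on eGFR, the gap adds events in about 0.4–4.1% of patients above kappa and essentially none below it. The primary 6MWT analysis is untouched and Type I error is not inflated.

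Two smaller points accompany it:

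- **Waiver.** SAP 10.2 does not name the last scheduled assessment. Note c to Table D 1 points to Week 24, while SAP 2.2.1 defines study completion through Week 28. In the simulation with no effect, moving the waiver to Week 28 changes P from 8.7% / 20.5% to 9.1% / 21.6%, that is 0.4–1.1 points.
- **Section 17.** It attributes the functional conditions to the protocol, which has none. The SAP governs, so the analysis does not change.

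**What to change.** Before unblinding:

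1. **Criterion 4.** Attach criterion 3's condition: no worsening of WHO class and no more than a 15% fall in 6MWT. WHO class and chemistry are scheduled at Weeks 1, 2 and 6, but the response in SAP 11.1.1 is taken "at each study visit where the 6MWT is measured (Week 4, Week 8, Week 16, and Week 24". State one rule for visits with no walk or a missed walk, such as the most recent 6MWT, and apply it to criteria 1 and 3 as well. The rule should say whether walks that 11.1.1 sets to missing after clinical worsening count here.
2. **Sensitivity analysis.** Repeat the composite without eGFR, unless redacted text already provides this. It is the part that addresses eGFR-only events in functionally stable patients.
3. **Minor.** State that the last-visit waiver refers to Week 24, and whether it applies when a missing end date is set to Study Drug Termination.
4. **Editorial.** List the WHO-class and 6MWT conditions in Section 17 as SAP changes.

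The cost is SAP wording and one sensitivity analysis, with no new data. There will be slightly fewer events, and criterion 4 will depend on having a walk value. Protocol 9.10.26 allows walks to be omitted in deteriorated patients, so a carried-forward value may miss a decline. The WHO-class part of the condition still applies at those visits.
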